8.6 Statistical Methods

Statistical testing and inference for efficacy and safety analyses are described in 8.6.1 and 8.6.2, respectively. Nominal p-values may be computed for other efficacy analyses as a measure of strength of association between the endpoint and the treatment effect rather than formal tests of hypotheses. All statistical tests will be conducted at $\alpha=0.05$, two-sided.

8.6.1 Efficacy Analysis

This section describes the statistical methods that address the primary and secondary objectives.

The estimand for the primary analysis approach for HbA1c and FPG consists of the following elements:

- Target population: Japanese patients with T2DM who have inadequate glycemic control on insulin monotherapy.
- Endpoints: mean change from baseline at Week 16 in HbA1c and in FPG.
- Measure of intervention effect: Difference in means in the effect of randomized treatments if all subjects followed the randomized treatment (without the addition of any other AHAs) through Week 16.

For the analysis of the primary endpoint (i.e., change from baseline in HbA1c at Week 16) in the FAS population, a constrained longitudinal data analysis (cLDA) method proposed by Liang and Zeger [12] will be used. This model assumes a common mean across treatment groups at baseline and a different mean for each treatment at each of the post-baseline time points. In this model, the response vector consists of baseline values and the values observed at each post-baseline time point. Time is treated as a categorical variable so that no restriction is imposed on the trajectory of the means over time. The analysis model will adjust for treatment, prior AHA therapy status (yes/no), time and the interaction of time by treatment, time by prior AHA therapy status and time by treatment by prior AHA status. The primary hypothesis which is the superiority of omarigliptin to placebo on mean HbA1c change from

baseline at Week 16 will be demonstrated using above cLDA model. The Kenward-Roger adjustment will be used with restricted (or residual) maximum likelihood (REML) to make proper statistical inference. An unstructured covariance matrix will be used to model the correlation among repeated measurements and hence avoids the potential bias that could result from the use of specific structured covariance models. If the unstructured covariance model fails to converge with the default Newton-Raphson algorithm, the Fisher scoring algorithm or other appropriate methods can be used to provide initial values of the covariance parameters. In the rare event that none of the above methods yield convergence, a structured covariance such as Toeplitz can be used to model the correlation among repeated measurements. In this case, the empirical option will be used because the sandwich variance estimator is asymptotically unbiased while the model-based variance estimator can grossly overestimate or underestimate the true variance. The cLDA model uses the maximum likelihood principle to estimate the parameters and account for missing data in an implicit fashion.

To avoid the confounding influence of rescue therapy on efficacy comparisons at Week 16, efficacy analyses in the FAS and PP populations will treat data as missing after the initiation of rescue therapy. Sensitivity analyses will be performed to assess the robustness of the results to the assumptions about missing data. The details will be described in sSAP.

Secondary efficacy endpoint of FPG at Week 16 will be analyzed using the above cLDA method described for HbA1c in the same fashion.

Analyses in the PP population for the primary and secondary efficacy endpoints at Week 16 will be performed using a repeated measures analysis of covariance (RM ANCOVA), in which the response vector consists of change from baseline at each of the post-baseline time points. The model will include the same terms for the cLDA model above, and baseline value as a covariate.

For the analysis of percentages of individuals at the HbA1c goals of <7.0% and <6.5% at Week 16, the constrained longitudinal data analysis (cLDA) model that is used for the analysis of HbA1c will also be used to impute Week 16 missing data on HbA1c. Imputations of the missing data will be based on the marginal univariate normal distributions with means equal to the predicted values and variances equal to the squared standard errors for the predicted values from the cLDA model. Ten sets of imputations of each missing value will be constructed from the cLDA model. The seed for the random number generator will be 3102039. Observed data will not be imputed. Subjects will be categorized as a responder (satisfying the HbA1c specific goal of <7.0% or <6.5%) or non-responder at Week 16 after imputations.

To estimate the within-group response rates and between-group rate difference, each of the 10 imputed data sets will be summarized to obtain the proportion of responders within each group. The estimated proportions of responders from the 10 imputed data sets will be combined using the standard multiple imputation (MI) techniques [14] to yield an overall estimate of response rate and associated variance for each group. The estimated response rates and effective sample sizes [15] will then be used to obtain the confidence intervals for within-group response rates via the Wilson score method [16], and the confidence interval and p-value for between-group rate difference via Miettinen & Nurminen (M&N) method [13].

Other efficacy secondary endpoint of change from baseline in 1,5-anhydroglucitol at Week 16 will be analyzed using the above cLDA method described for HbA1c in the same fashion.

Table 10 summarizes the key efficacy analyses. The strategy to address multiplicity issues with regard to multiple endpoints is described in Section 8.8, Multiplicity.

Table 10 Analysis Strategy for Key Efficacy Variables

Endpoint	Approach	Statistical Method	Analysis Population	Missing Data Approach
Primary				
Change from baseline in HbA1c at Week 16	P	cLDA	FAS	Model-based
	S	RM ANCOVA	PP	N/A
	S	Missing Data Methods [§]	§	§
Secondary				
Change from baseline in FPG at Week 16	P S	cLDA RM ANCOVA	FAS PP	Model-based N/A
Percentages of subjects at HbA1c goals (<7.0% and <6.5%) at Week 16	P	M&N	FAS	MI
Change from baseline in 1,5-AG at Week 16	P	cLDA	FAS	Model-based
Change from baseline in HbA1c at Week 52	P	Summary Statistics	FAS	N/A
Change from baseline in FPG at Week 52	P	Summary Statistics	FAS	N/A
Percentages of subjects at HbA1c goals (<7.0% and <6.5%) at Week 52	P	Summary Statistics	FAS	N/A
P=Primary; S=Secondary.				
§ Sensitivity analyses will be performed to assess the impact of missing data. Details will be provided in the sSAP.				

For long-term efficacy data up to Week 52, the mean change and the 95% confidence intervals will be calculated by treatment groups of double-blind period to assess the long-term efficacy of omarigliptin. The mean change will be computed relative to baseline (Visit 4/Day 1/Randomization). Between-groups comparisons and/or estimation of between-group difference will not be performed.

For the HbA1c goals of <7.0% and <6.5% at Week 52, the percentage of individuals and the 95% confidence intervals will be calculated using Wilson score method [16] by treatment groups of double-blind period.

For long-term efficacy analyses, all data will be included in the analysis regardless of initiating the rescue therapy since insulin dose during extension period are allowed to down or up –titrate if clinically required.

The summary statistics for the insulin dose, percentages of subjects with up-titration and down-titration of insulin dose will be generated by treatment group of double-blind period at Week 16 and Week 52.

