5.5 Concomitant Medications/Vaccinations (Allowed & Prohibited)

Medications or vaccinations specifically prohibited in the exclusion criteria are not allowed during the ongoing trial. If there is a clinical indication for any medication or vaccination specifically prohibited during the trial, discontinuation from trial therapy or vaccination may be required. The investigator should discuss any questions regarding this with the Sponsor Clinical Director. The final decision on any supportive therapy or vaccination rests with the investigator and/or the subject's primary physician. However, the decision to continue the subject on trial therapy or vaccination schedule requires the mutual agreement of the investigator, the Sponsor and the subject.

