5.5.1 Prohibited medications

- (1) All AHAs (Except for omarigliptin for the trial and insulin agents which will be administered during the trial)
 - a) Insulin agents [rapid-acting, ultra rapid-acting insulin or pre-mixed insulin/fixed ratio combination of insulin (content percentage of rapid-acting or ultra rapid-acting insulin is greater than 30%)]
 - b) SUs (sulfonylureas, sulfonamides)
 - c) Glinides (nateglinide, mitiglinide, repaglinide, etc.)
 - d) BGs
 - e) TZD
 - f) α -GIs
 - g) DPP-4 inhibitors
 - h) SGLT2 inhibitors
 - i) GLP-1 receptor agonists (Such as exenatide or liraglutide)
 - j) FDC products containing the above active ingredient(s) (Except for insulin agents which will be administered during the trial)

<Note> The subject in Group A can continue single oral AHA taken at Visit 1/Screening thorough to Visit 2/Week -10.

- (2) Other investigational drugs

- (3) Systemic corticosteroids \geq 14 consecutive days or repeated courses

<Note> Inhaled, nasal, and topical corticosteroids which don't have systemic effect are permitted.

Within 10 hours before the visit

- (1) Intravenous fluids (other than those having a volume <50 mL without any glucose content)
- (2) Glucagon

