5.6 Rescue Medications & Supportive Care

5.6.1 Rescue treatment (up-titration of insulin)

The subject who meets the following glycemic rescue criteria in [Table 4](#) should initiate rescue therapy with up-titration of the insulin that they are receiving during the trial (continuing from Visit 1/Screening).

Table 4 Rescue criteria

Application Timing	Criteria	Administration Timing
After Visit 4/Day 1/Randomization to Visit 10/Week 24	FPG (as reported by the central lab) is repeatedly * confirmed >240 mg/dL two times	At the next scheduled or unscheduled Visit (= Rescue Visit)
After Visit 10/Week 24	FPG (as reported by the central lab) is repeatedly * confirmed >200 mg/dL two times	

* Repeatedly at the scheduled visit (or at unscheduled visit as needed).
After initiation of rescue therapy, insulin can be adjusted by judgment of the investigator even if the FPG does not show "repeatedly" the above criteria.

Subjects that meet rescue criteria will have their insulin dose adjusted as determined clinically appropriate by the investigator to manage glycemic control. The maximum dosage of insulin should follow the maximal approved dose based on its package insert.

During Phase A, up-titration of insulin relative to the dose at Visit 4/Day 1/Randomization may be performed only if the subject has glucose measurements meeting rescue criteria, during Phase B, up-titration will be determined by investigator's assessment of subject's need for glycemic control.

Subjects will continue on study medication after initiation of rescue therapy or down-titration of insulin until completion unless they meet discontinuation criteria (See Section 5.8).

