o In addition, investigator's decision that subject should discontinue for any other reason.

Example: Requirement for one of the excluded medications listed in Section 5.5.

If a subject discontinues study medication, he/she should complete all Discontinuation Visit procedures as listed in the Trial Flow Chart (see Section 6.0). All subjects will be followed until resolution (i.e., return to baseline values, diagnosis determined or new stable state established, based upon investigator and the Sponsor) for any adverse events or any laboratory safety test abnormality resulting in discontinuation from study medication.

Discontinuation from treatment is "permanent." Once a subject is discontinued, he/she shall not be allowed to restart treatment.

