7.1.4 Other Procedures

7.1.4.1 Withdrawal/Discontinuation

When a subject discontinues/withdraws from participation in the trial, all applicable activities scheduled for the Visit 15/Week 52 should be performed at the time of discontinuation. Any adverse events which are present at the time of discontinuation/withdrawal should be followed in accordance with the safety requirements outlined in Section 7.2 - Assessing and Recording Adverse Events.

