To avoid the confounding influence of rescue therapy on efficacy comparisons at Week 16, efficacy analyses in the FAS and PP populations will treat data as missing after the initiation of rescue therapy. Outlines on the approach to handling missing data are provided in Section 8.6, Statistical Methods. Sensitivity analysis to assess the impact of missing data will be described in sSAP.

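### The HbA1c and FPG estimand excludes added AHAs, but the primary FAS analysis removes data only after insulin rescue, so values after a prohibited AHA stay in

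*Combined protocol and SAP*

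**What the plan says.** **Estimand.** Section 8.6.1 states the intervention effect for HbA1c and FPG as the difference in means "if all subjects followed the randomized treatment (without the addition of any other AHAs) through Week 16".

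**Data rule.** Sections 8.5.1 and 8.6.1 both say that "efficacy analyses in the FAS and PP populations will treat data as missing after the initiation of rescue therapy". No other event sets Week 16 efficacy data to missing.

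**Rescue.** Under Section 5.6.1, a subject who meets the glycemic criteria "should initiate rescue therapy with up-titration of the insulin that they are receiving during the trial".

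**Prohibited AHAs.** Section 5.5.1 lists the other glucose-lowering classes and also some insulins: "Insulin agents [rapid-acting, ultra rapid-acting insulin or pre-mixed insulin/fixed ratio combination of insulin" (for the pre-mixed products, those with more than 30% rapid-acting content).

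**What happens to such a subject.** Section 5.5 says discontinuation may be required, and that "the decision to continue the subject on trial therapy or vaccination schedule requires the mutual agreement of the investigator, the Sponsor and the subject". Section 5.8 gives need for an excluded medication as an example of a reason for the investigator to stop treatment. It adds: "If a subject discontinues study medication, he/she should complete all Discontinuation Visit procedures as listed in the Trial Flow Chart". Note 7 to the Section 6.0 flow chart omits the HbA1c draw at that visit only within 4 weeks of randomization.

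**Populations.** The FAS needs one dose and one measurement. The PP set drops a subject at all time points for prohibited AHA use of 7 or more consecutive days or 14 or more days in total. Section 8.5.1 commits the sponsor to investigate substantial differences between FAS and PP conclusions, and says: "Sensitivity analysis to assess the impact of missing data will be described in sSAP".

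**The concern.** The one intercurrent event that the estimand names, addition of another AHA, has no rule in the primary analysis. The event that does have a rule, up-titration of existing insulin, is not clearly named in the estimand. The cLDA response vector holds every observed post-baseline value that the rescue rule does not remove. A value lowered by a prohibited AHA is therefore analysed as if it came from randomized treatment and background insulin alone. No sentence says that such values are kept. It follows from the absence of any rule to remove them.

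The HbA1c-goal analysis inherits the gap, because it uses the same HbA1c values and imputes only those that are missing.

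At stake is what the primary estimate means. The direction of any bias depends on the arm: toward zero if placebo subjects take the drug, away from zero if omarigliptin subjects do.

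**Working it through.** **1. The plan's own figures.** Inputs from Section 8.9: 120 and 60 subjects; cumulative attrition 0.0125, 0.0250, 0.0375 and 0.0500; the stated conditional correlation matrix; conditional SD 0.82; two-sided alpha 0.05.

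- Summing the information over the monotone missing-data patterns gives effective sample sizes of 117.33 and 58.67, total 176.0 (plan: 176).
- SE = 0.82 × √(1/117.33 + 1/58.67) = 0.1311. Half-width = 1.96 × 0.1311 = 0.257 (plan: 0.26).
- Power at a difference of 0.50, noncentral t with 174 df: 96.7% (plan: 97%).

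The planning figures reproduce. The point concerns the match between estimand and analysis, not arithmetic.

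**2. Effect of a kept value.** The documents give no rate of prohibited AHA use and no effect size for it. Assume that the drug lowers Week 16 HbA1c by *d* = 0.5 to 1.0 points and that the kept value carries the full fall. The shift is *m* × *d* / *n* for *m* users in an arm of *n*.

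| Users, none in the other arm | Shift in the difference | In SE units | Power at a true 0.50 |
|---|---|---|---|
| 1 placebo, *d* = 0.5 | 0.5/60 = 0.008, smaller | 0.06 | 96.2% |
| 1 placebo, *d* = 1.0 | 1.0/60 = 0.017, smaller | 0.13 | 95.6% |
| 3 placebo, *d* = 1.0 | 3.0/60 = 0.050, smaller | 0.38 | 92.7% |
| 1 omarigliptin, *d* = 0.5 | 0.5/120 = 0.004, larger | 0.03 | – |
| 1 omarigliptin, *d* = 1.0 | 1.0/120 = 0.008, larger | 0.06 | – |

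Dividing by the effective placebo size of 58.67 instead of 60 gives 0.0085 to 0.0170, which is no material change.

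The plan's 90% power point is a difference of 0.43, so power falls below 90% after a shift of about 0.07. That needs 0.07/(1.0/60) = 4.2, so 5 placebo users at *d* = 1.0, or 0.07/(0.5/60) = 8.4, so 9 at *d* = 0.5, with none on omarigliptin. This is 5/60 = 8% to 9/60 = 15% of the placebo arm.

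**3. FPG.** SE = 48 × √(1/117.33 + 1/58.67) = 7.68 mg/dL. With an assumed fall of 20 to 50 mg/dL, each placebo user shifts the difference by 20/60 = 0.33 to 50/60 = 0.83 mg/dL, or 0.04 to 0.11 SE.

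**4. Price of removing the values.** Same information calculation, with extra placebo values set to missing:

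| Extra missing in the placebo arm | Placebo effective N | SE | Rise in SE | Power at 0.50 |
|---|---|---|---|---|
| 1 subject, Week 16 only | 58.54 | 0.1312 | 0.07% | 96.6% |
| 3 subjects, only Week 4 kept | 57.37 | 0.1321 | 0.75% | 96.4% |
| 3 subjects, no post-baseline value kept | 55.67 | 0.1335 | 1.8% | 96.1% |

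**The case against.** **Few such values may exist.** Subjects with poor control already have a permitted route in insulin up-titration. Section 5.8 offers need for an excluded medication as an example of a reason to discontinue, and discontinuation is permanent. This stands as to frequency. It does not remove the route by which a subject continues under Section 5.5.

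**Discontinuation Visit values.** A reader might infer that every HbA1c drawn at that visit after a prohibited AHA enters the primary model. Section 7.1.4.1 does say that "all applicable activities scheduled for the Visit 15/Week 52 should be performed at the time of discontinuation", but the flow chart gives the visit its own column and no rule in the documents maps it to Week 4, 8, 12 or 16. Such a value counts only if it is mapped. It would be at most one per subject and need not carry the full fall assumed above.

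**The PP analysis addresses this event.** It does, and the promise to investigate FAS–PP differences is a real safeguard. It is partial: the analysis is secondary, uses a different model (RM ANCOVA), drops whole subjects and does not change the primary estimate.

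**The sSAP may cover it.** It is not among the documents. What they assign to it on this point concerns missing data, and a retained value is not missing. One cannot conclude that it will be silent.

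**The parenthesis may simply mean rescue.** A reader might infer that the rescue rule contradicts the estimand. It does not. The documents elsewhere treat insulin as an AHA, so the wording may or may not take in extra background insulin. That is ambiguity, and it leaves rewording the estimand as a legitimate repair.

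**Conclusion.** The mismatch holds. Followed as written, the primary analysis can include HbA1c and FPG values that its own estimand excludes, mainly from subjects allowed to continue after starting a prohibited AHA.

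Its expected size is small: about 0.06 to 0.13 SE per placebo user for HbA1c. This rests on the assumed 0.5 to 1.0 point fall, a kept Week 16 value and use in one arm only; use in both arms would partly offset. A reader might infer that the superiority test is at risk. The figures do not support that. Power falls below 90% only with 5 to 9 placebo users and none on omarigliptin, whereas the plan allows for 5% cumulative attrition by Week 16, post-rescue data included, which is 3 of 60 placebo subjects.

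The change is still worth making, because it lets the primary estimate mean what Section 8.6.1 says at almost no loss of precision.

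**What to change.** **Preferred.** In Sections 8.5.1 and 8.6.1, state that the primary FAS analyses of HbA1c and FPG, and the HbA1c-goal analysis, also treat data as missing after initiation of a prohibited AHA.

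- *Trigger.* The PP thresholds already in Section 8.5.1, with missingness dated from the first day of the qualifying use, are suitable and keep the FAS and PP rules consistent. A stricter rule based on any use is the sponsor's choice. It would make the FAS stricter than the PP set for brief use unless the PP rule is changed too.
- *Estimand.* In the same edit, name rescue up-titration of background insulin alongside addition of another AHA. This does not change the estimate.

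**Alternative.** If the parenthesis was meant only to describe rescue, reword the estimand to match the rescue-only rule and leave the analysis as it is.

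**Timing.** Decide before unblinding. Section 8.0 requires a protocol amendment if the methods for the primary hypothesis change once the study has begun.

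**Cost.** No new data or model is needed, because Section 7.1.1.5.2 already has concomitant medication recorded. The analysis leans slightly more on missing at random. With three such placebo subjects the SE rises by 0.75% if Week 4 is kept and by 1.8% if all post-baseline values are lost, and power at 0.50 stays at about 96%.

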8.0 STATISTICAL ANALYSIS PLAN

This section outlines the statistical analysis strategy and procedures for the study. If, after the study has begun, but prior to unblinding, changes are made to the primary and/or key secondary hypothesis, or the statistical methods related to those hypotheses, then the protocol will be amended (consistent with ICH Guideline E-9). Changes to exploratory or other non- confirmatory analyses made after the protocol has been finalized, but prior to unblinding, will be documented in a supplemental Statistical Analysis Plan (sSAP) and referenced in the Clinical Study Report (CSR) for the study. Post hoc exploratory analyses will be clearly identified in the CSR.

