8.8 Multiplicity

The primary evaluation of the glycemic efficacy in this study will be based on testing the primary hypotheses for HbA1c at Week 16. Since there is only one primary hypothesis, no multiplicity adjustment will be needed.

Comparisons involving other efficacy endpoints are considered supportive or exploratory and will be made at $\alpha=0.05$ nominal level (two-sided) and 95% CIs will be provided. No multiplicity adjustment will be performed for these other comparisons.

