8.9 Sample Size and Power Calculations

Efficacy analyses

A sample size of 180 subjects in a 2:1 ratio (i.e., 120 and 60 subjects for omarigliptin and placebo, respectively) will be equivalent to an effective sample size of 176 at Week 16 in the power calculation for the primary hypothesis test using the cLDA model. The effective sample size accounts for information loss due to missing data and the correlation among repeated measures, and is derived using the method proposed by Lu, et al. [17] under the assumptions of cumulative attrition rates and covariance matrix at Weeks 4, 8, 12, and 16 specified below. An effective sample size of 176 will provide 97% power to detect a treatment difference of 0.5% at Week 16 ($\alpha=0.05$, two-sided test) assuming the conditional standard deviation is 0.82%. In addition, it will provide 90% (80%) power to detect a treatment difference of 0.43% (0.37%). The half-width of the 95% CI is expected to be 0.26%. These calculations were based upon the following assumptions:

- Cumulative attrition rates, which include HbA1c data considered missing after rescue, at Weeks 4, 8, 12, and 16 are 0.0125, 0.0250, 0.0375, 0.0500, respectively
- A conditional correlation matrix at Weeks 4, 8, 12, and 16 is

$$\begin{bmatrix} 1.0 & 0.91 & 0.83 & 0.77 \\ 0.91 & 1.0 & 0.93 & 0.87 \\ 0.83 & 0.93 & 1.0 & 0.94 \\ 0.77 & 0.87 & 0.94 & 1.0 \end{bmatrix}$$

The cumulative attrition rates and correlation assumptions above are based on data from MK-0431 PN106.

Given the effective sample size above, the treatment difference of 25.0 mg/dL (21.6 mg/dL) can be detected with 90% (80%) power for the secondary efficacy endpoint, change from baseline in the fasting plasma glucose (FPG) at Week 16, assuming the conditional standard deviation is 48 mg/dL.

Safety analyses

The sample size is expected to provide 100 or more subjects exposed for one year (omarigliptin group only), assuming 15% discontinuation rate for 52 weeks.

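### Does the imputation for the HbA1c goals leave out subject-level variance because its standard error is not defined?

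*Combined protocol and SAP*

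**What the plan says.** Section 8.6.1 imputes missing Week 16 HbA1c for the goal endpoints from the same cLDA model as the primary analysis. On the distribution it says "Imputations of the missing data will be based on the marginal univariate normal distributions", centred on the predicted values and with "variances equal to the squared standard errors for the predicted values from the cLDA model". It continues: "Ten sets of imputations of each missing value will be constructed from the cLDA model". Observed values are left alone, and the random seed is fixed.

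The ten sets are combined by standard multiple-imputation rules, and then "The estimated response rates and effective sample sizes [15] will then be used to obtain the confidence intervals for within-group response rates" by the Wilson method. The between-group difference is handled by Miettinen and Nurminen.

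Section 8.9 sets expected missingness at Week 16 to 5%, and that figure already covers values discarded after rescue: "Cumulative attrition rates, which include HbA1c data considered missing after rescue". Section 3.2 attaches no hypothesis to the goal objective. Section 8.8 describes its status: "Comparisons involving other efficacy endpoints are considered supportive or exploratory", tested at a nominal level.

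**The concern.** Two things needed to program the step are not stated: what the prediction conditions on, and which standard error is meant. A statistician who reads the sentence as the standard error of a fitted mean sees a known mistake. Proper multiple imputation draws from the predictive distribution of the individual value, whose variance is the residual variance plus parameter uncertainty. Using only the parameter part makes the draws far too tight.

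In the extreme version, every missing subject gets the arm mean plus a little noise. All ten draws then fall on the same side of 7.0%, the between-imputation variance is zero, and the procedure becomes non-responder imputation. The effective sample sizes passed to Wilson and to Miettinen and Nurminen stay at 120 and 60, as if nobody were missing. At stake are intervals that are too short and a response rate biased downward in both arms, for a listed secondary endpoint that is reported with a confidence interval and a p-value.

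**Working it through.** **Inputs from section 8.9:** 120 and 60 subjects; conditional SD 0.82%; cumulative missingness 1.25%, 2.5%, 3.75% and 5% at Weeks 4, 8, 12 and 16; the 4 x 4 conditional correlation matrix.

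**The plan's own figures reproduce.** Generalised least-squares information under monotone dropout gives an effective N of 176.0 (stated 176). The SE of the difference is 0.82 x sqrt(1/117.3 + 1/58.7) = 0.131. Power for a difference of 0.5% is 96.8% (stated 97%), and the half-width is 1.96 x 0.131 = 0.257 (stated 0.26).

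**Size of the term in question**

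- SE of a fitted Week 16 mean: 0.82/sqrt(117.3) = 0.076 (omarigliptin) and 0.82/sqrt(58.7) = 0.107 (placebo).
- Predictive SD of one missing value, 0.82 x sqrt(1 - R²), with R² from regressing Week 16 on all earlier visits:

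| Last observed HbA1c | R² | Predictive SD |
|---|---|---|
| Week 12 | 0.884 | 0.279 |
| Week 8 | 0.760 | 0.402 |
| Week 4 | 0.593 | 0.523 |
| Baseline only | 0 | 0.82 |

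The ratio runs from 0.279/0.107 = 2.6 to 0.82/0.076 = 10.8. For a predicted value of 7.6%, the chance that a draw falls below 7.0% is about 0.00000001 with SD 0.107, against 0.016 to 0.232 with the predictive SDs. So the two readings really are different programs.

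**What it does to the result at 5% missing.** A hand check bounds the shift. If every missing subject is forced to non-response and missingness is random, an arm's rate falls by the missing fraction times its response rate. With assumed rates of 24.0% and 11.4% for <7.0%, that is 0.05 x 24.0 = 1.2 points and 0.05 x 11.4 = 0.57 point. The difference falls by about 0.63 point.

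Simulation agrees (4,000 trials per setting, 10 imputations, Rubin variance). The following are assumed, because the documents do not give them: baseline mean 8.2 to 8.8%, baseline SD 0.7, slope 0.8, arm changes of 0 to +0.1 and -0.5 to -0.6, missing at random, effective n = p(1-p)/V. One setting, baseline 8.5% and goal <7.0%:

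| Draws | Rate difference | Mean reported SE | Actual SD of estimate | Effective n |
|---|---|---|---|---|
| Subject-specific, no residual | 9.19% | 4.53 | 4.60 | 119.5/59.7 |
| Arm mean, no residual | 8.82% | 4.45 | 4.54 | 120.0/60.0 |
| Subject-specific, predictive | 9.28% | 4.62 | 4.59 | 116.6/57.9 |
| Arm mean, predictive | 9.27% | 4.68 | 4.53 | 113.8/56.1 |

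Without the residual, the reported SE is too small against the actual spread of the estimate by 1.5% (4.53/4.60 = 0.985) or 2.0% (4.45/4.54 = 0.980). With full predictive draws it is 0.7% or 3.3% too large.

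**Error rates.** Under no treatment difference, type I error at 5% missing is 0.044 to 0.050 without the residual term and 0.035 to 0.039 with it. At 20% missing it is 0.047 to 0.053 without and 0.013 to 0.027 with. The Monte Carlo SE is sqrt(0.05 x 0.95/4000) = 0.003.

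**Coverage.** A second simulation (2,500 runs per setting, slope 0.7, placebo Week 16 mean 8.2 or 8.5%, no strata, same effective-n formula) gives, for <7.0% and random missingness, half-widths 2.0-4.0% too narrow. Coverage is 93.9-95.0% without the residual, against 95.4-95.6% with it. For <6.5% the half-widths are 3.4-5.9% too narrow, but coverage without the residual is 95.0% or more. If the missing subjects mainly have high HbA1c, as after rescue (Phase A rescue requires that "FPG (as reported by the central lab) is repeatedly * confirmed >240 mg/dL two times"), they are non-responders under either draw. The <7.0% half-width then changes by 0.2%.

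**The case for a change.** The strongest case for acting is that section 8.6.1 fixes the seed and the number of imputations, so it aims at a reproducible procedure, yet leaves open the distribution, which matters more. The sSAP is cited for missing-data sensitivity analyses of the primary endpoint, not for this step. The 5% rate is borrowed from another trial. At 20% missing, the arm-mean reading would lower the rate difference by 1.8 points and make the SE about 19% smaller than under predictive draws. A choice made after Week 16 unblinding would be post hoc, and one sentence would prevent that.

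The ambiguity is real and that part stands, as does the growth of the shift with missingness. Two things weaken the rest. First, the text never speaks of a fitted mean. It speaks of predicted values used to fill each missing value, which fits a prediction standard error at least as well. The word marginal can simply mean the Week 16 component of the subject's joint predictive distribution, since only Week 16 is imputed. The most striking consequences (all draws above 7.0%, zero between-imputation variance) need the arm-mean reading. Second, a narrower interval matters through coverage and type I error. Type I error stays nominal even at 20% missing, and the bias runs against the drug.

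**Conclusion.** The plan leaves a term undefined, but no rule it states is shown to give a wrong result. If the prediction standard error given the subject's own HbA1c is meant, nothing is wrong. If the standard error of a fitted mean were used, the cost at the planned 5% missing would be an interval for the <7.0% difference about 2-4% too narrow with coverage near 94-95%, a rate difference at most about 0.7 point too low, and no type I error inflation. The cost nearly disappears if the missing values are mostly post-rescue. Full predictive draws would exchange slight undercoverage for slight conservatism.

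These sizes depend on the 5% rate, on assumed baseline and response levels, and on p(1-p)/V as the effective sample size, a formula the documents cite but do not print. The endpoint has no hypothesis, its test is nominal, and the primary cLDA analysis is untouched. An experienced analyst would draw from the conditional predictive distribution. Section 8.0 already lets changes to non-confirmatory analyses be recorded in the sSAP before unblinding. This is a gap that analysts fill sensibly, and no change to the plan is needed.
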